11.3 STATISTICAL ANALYSIS

11.3.1 Methods of Statistical Analysis

The planned analyses will include descriptive statistics on response rates, biomarkers, and the incidence and severity of adverse events. The proportions of treatment related adverse events and their severity will be estimated using the sample proportions, and their inferences including confidence intervals and hypotheses testing will be evaluated using Binomial distributions. The time to adverse events will be analyzed using appropriate tools in survival analysis such as Kaplan-Meier estimates. Graphical tools will be used to display the appropriate estimates.

11.3.2 Sample Size

Let p be the probability of subjects reaching day +56 without a TRSAE. The sample size is determined by testing the null hypothesis $H_0 : p = 75\%$ versus the alternative hypothesis $H_a : p > 75\%$ with a one-sided significant level of 0.05. Based upon our previous phase 1 trial (12-H-0010), the TRSAE rate was 0 out of 10 subjects and we expect 95% subjects would reach day +56 without a TRSAE. Thus a sample size of 23 subjects will achieve 89.5% power to test the above hypotheses using an exact binomial test.

To account for the possibility of non-treatment related drop out, up to 2 additional subjects may be enrolled to replace those subjects that are non-evaluable for the study's primary endpoint for a total accrual of 25 patients. At an accrual rate of 1-2 subjects per month, this study will be completed in 12-18 months.

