The Cell Processing Section of the Department of Transfusion Medicine at the Clinical Center NIH has developed a BMSC repository at NIH. The NIH BMSC are a third party, early passage product based on the EU manufacturing approach. The NIH BMSC cellular product was administered safely to transplant recipients with steroid-resistant acute GVHD in a phase I study (protocol 12-H-0010, IND #14596) conducted from March 2012 to October 2012 at NIH. This pilot study is a continuation of the previous study and open to allogeneic stem cell transplantation recipients at NIH (age ≥ 4 yrs) with *de novo* acute GVHD requiring systemic therapy, either directly after allogeneic transplantation or following treatment with donor lymphocyte infusion. Subjects will receive BMSC infusions (target dose of 2×10^6 BMSC/kg for up to 12 doses) in addition to standard upfront therapy with corticosteroids. The primary endpoint will be the proportion of patients without a treatment-related severe adverse event (TRSAE) at day +56. Responses will be assessed at day +28 and +56 from the initial diagnosis. Responses will be correlated to changes in GVHD biomarkers including ST2, Reg3a, TNFR1, and IL-6. Subjects will be enrolled at first diagnosis of acute GVHD, and the first BMSC infusion will be given within 120 hours of the first dose of corticosteroids. BMSC infusions will be given twice weekly for the first 4 weeks. Subjects with a complete response at the end of week 4 will not receive further infusions. All other subjects will receive BMSC infusions weekly for four additional weeks. Safety will be monitored continuously with a stopping rule for toxicity based on the treatment-related serious adverse event rate. Research samples will be drawn at regular intervals to explore biological correlates of response and to investigate the mechanism of action of BMSC.

Abbreviated Title: Early BMSC Pilot for Acute GVHD

Version Date: 6/16/2016

TABLE OF CONTENTS

1. INTRODUCTION	5
1.1 Study Objectives	5
2. BACKGROUND	5
2.1 Acute Graft-versus-Host Disease	5
2.2 Primary Therapy for Acute GVHD	6
2.3 Biology of Bone marrow-derived mesenchymal stem cells.....	6
2.4 Clinical Experience With BMSC in GVHD	7
2.5 NIH Phase I BMSC Trial (12-H-0010).....	10
2.6 Safety Of BMSC Infusions	11
2.7 Scientific And Clinical Justification	12
2.8 Rationale for Changes from Phase I Study	12
3. STUDY DESIGN.....	14
3.1 Study Design	14
3.2 Subject Inclusion	14
3.3 Initial Assessment	14
3.4 Treatment	15

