2.6.1 Safety of the NIH BMSC Product

The phase I study met the primary objective of safety³⁹. Protocol defined treatment-related SAE was encountered by none of the subjects. Infusion reactions were seen in one subject (grade 1 pruritus). There was one death while on study (gram-negative bacterial sepsis). There were seven serious adverse events: bacterial infection (n=5), gastrointestinal bleeding (n=1), and a mucus plug in the respiratory tract (n=1). In addition, there were 13 non-SAEs: grade 1 (n=7), grade 2 (n=4), and grade 3 or 4 (n=2). None of these adverse events were attributable to the BMSC product. The HLA antibody screen remained negative prior to and immediately after completing the BMSC trial. New CMV reactivation without the development of CMV organ diseases occurred in two patients, controlled by pre-emptive antiviral therapy.

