3.4.2.4 Missed infusions

Unanticipated logistical challenges including, but not limited to, adverse weather, availability of transportation, or equipment-related delays may occur. Subjects can miss up to four (4) BMSC infusions in total over the course of the treatment protocol and remain enrolled and evaluable for response. If an infusion or series of infusions are missed, the infusion will not be rescheduled and the subject will go on to receive the next scheduled infusion in the treatment course. Subjects missing more than four (>4) BMSC infusions will be removed from the treatment protocol and will not be evaluable for the primary endpoint.

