8.3 TREATMENT LIMITING TOXICITIES

The observational period for determining Treatment Limiting Toxicities is from the initiation of the BMSC infusion to 3 weeks after the last infusion. A treatment related serious adverse event (TRSAE) is defined as an SAE which is at least probably or definitely related to the BMSC infusions. Any subject who encounters a TRSAE will not receive further infusions.

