11. BIOSTATISTICAL CONSIDERATIONS

11.1 PRIMARY ENDPOINT

The primary endpoint of this study is:

- The proportion of subjects reaching day +56 without a TRSAE.

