11.3.4.2 For Safety

The trial will be monitored for safety based on Treatment Related Serious Adverse Events (TRSAE), which is also the primary endpoint of the study. A TRSAE is defined as an SAE which is at least probably or definitely related to the BMSC infusions. The trial will be stopped if 3 subjects have developed one or more TRSAE's. This is based on the binomial test of the primary hypothesis (Section 11.3.2) and at least 21 of 23 subjects without a TRSAE are needed to reject the null hypothesis. If 3 or more subjects developed TRSAE's are observed, the null hypothesis will not be rejected and we will stop the study early.

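### The primary endpoint and its decision rule score some subjects differently, and the evaluability rules can remove subjects with an early TRSAE from the primary analysis

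*Combined protocol and SAP*

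**What the plan says.** Section 11.1 gives the primary endpoint as "The proportion of subjects reaching day +56 without a TRSAE". Section 11.3.2 defines p in the same terms, tests 75% against a higher rate at one-sided 0.05, and supports the alternative with 0 TRSAEs in 10 phase I subjects: "we expect 95% subjects would reach day +56 without a TRSAE". The précis omits the idea of reaching the day: "The primary endpoint will be the proportion of patients without a treatment-related severe adverse event (TRSAE) at day +56".

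Section 11.3.4.2 calls TRSAE the primary endpoint and states that "at least 21 of 23 subjects without a TRSAE are needed to reject the null hypothesis". The trial stops once three subjects have had a TRSAE. No day limit is attached to that count. Section 8.3 runs the observation period to 3 weeks after the last infusion, and section 11.2 puts the total at 7 to 11 weeks.

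Three provisions govern who is counted:

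- Section 3.4.2.4: "Subjects missing more than four (>4) BMSC infusions will be removed from the treatment protocol and will not be evaluable for the primary endpoint".
- Section 11.3.2: "up to 2 additional subjects may be enrolled to replace those subjects that are non-evaluable".
- Section 11.3.3: subjects with fewer than two completed doses are replaced.

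Section 8.3 adds: "Any subject who encounters a TRSAE will not receive further infusions". A TRSAE must be at least probably related to BMSC, so an unrelated or only possibly related death is not one.

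**The concern.** Section 11.3.4.2 presents the TRSAE count as the test of the section 11.1 endpoint, but they are different variables. Where they part, the plan does not say which governs, so the primary conclusion could depend on a choice made after outcomes are known in an open, single-arm trial.

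The evaluability wording raises a second problem. A subject whose infusions stop because of a TRSAE goes on to have doses not given. If those count as missed, or if fewer than two doses were completed, the subject leaves the primary analysis of a safety endpoint because of the event being counted. That biases the result toward rejecting H0.

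**Working it through.** **1. The plan's own figure.** Inputs from section 11.3.2: n=23, p0=0.75, p1=0.95, one-sided 0.05, exact binomial. Write X for the number of successes.

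- P(X≥21 | 23, 0.75) = 0.0492, and P(X≥20 | 23, 0.75) = 0.137, so the cut-off of 21 is right.
- P(X≥21 | 23, 0.95) = 0.8948, which reproduces the stated 89.5%.

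**2. Where the two rules disagree.**

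| Subject | 11.1 and 11.3.2 | 11.3.4.2 |
|---|---|---|
| (a) Evaluable, no TRSAE, dies or withdraws before day +56 | failure | success |
| (b) First TRSAE after day +56, within 3 weeks of last infusion | success | failure |

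Case (a) survives the missed-infusion rule. A subject who has had 8 doses has missed none if in complete response, and at most 12−8=4 otherwise. Four is within the allowance, so the subject stays evaluable.

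Case (b) can occur in subjects dosed weekly in weeks 5 to 8: day +56 is the end of week 8, and observation runs to week 11.

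**3. Effect on the conclusion.**

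- Case (a), 23 evaluable, no TRSAE, 3 such deaths: the section 11.1 wording gives 20/23, p=0.137, H0 not rejected. The TRSAE count gives 23/23, p=0.75^23=0.0013, rejected.
- Case (b), 23 evaluable, 2 TRSAEs by day +56 and 1 after it: the section 11.1 wording gives 21/23, p=0.049, rejected. The TRSAE count gives 20/23, not rejected, and the three-subject boundary is met.

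**4. Early TRSAEs leaving the analysis.** Suppose infusions stop after dose k because of a TRSAE. Against the 8-dose schedule, 8−k exceeds 4 for k≤3. Against the 12-dose schedule, 12−k exceeds 4 for k≤7. A TRSAE at the first dose also meets the replacement rule in section 11.3.3.

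The documents do not give the share s of TRSAE subjects who would be lost this way, so it is assumed. At the null (75% TRSAE-free, 25% with a TRSAE), the TRSAE-free proportion among those kept is 0.75/(1−0.25s). With 23 analysed and the rule at 21/23:

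| s | Rate among those kept | Type I error |
|---|---|---|
| 0 | 0.750 | 4.9% |
| 10% | 0.75/0.975 = 0.769 | 7.3% |
| 25% | 0.75/0.9375 = 0.800 | 13.3% |
| 50% | 0.75/0.875 = 0.857 | 34.2% |

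These figures also assume that removed subjects are left out of the three-subject stopping count.

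**5. Fewer than 23 analysed.** At n=22, 20/22 has a type I error of 0.0606, so 21/22 is needed (0.0149), with power 69.8% at p=0.95. Two TRSAEs then fail the test although the boundary of three is not reached. The boundary and the test agree at the planned 23 but not at 22.

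**The case against.** The best case for the plan is that freedom from TRSAE is plainly what was meant. The précis words it so, section 11.3.4.2 says so, and the 95% comes from a TRSAE rate. On that reading the 95% has the right basis and the power is correct. This stands.

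A reader might infer from the phrase about reaching day +56 that the endpoint is a composite with survival and that the trial is therefore underpowered. The documents do not support that: nothing else in the plan treats survival as part of success. A reader might also take the phase I report, "There was one death while on study (gram-negative bacterial sepsis", as showing that 95% is too high. It does not. That death is undated, occurred in a different population (mainly steroid-resistant GVHD), and was not attributed to BMSC.

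Deaths would also be visible. Section 3.7 assesses survival at day +56, section 11.3.4.1 halts accrual at each death within follow-up, section 9.2.2 takes subjects who die off study, and section 11.3.1 plans Kaplan-Meier estimates of time to adverse events. Section 9.2.3 hints that non-survivors may not be evaluable. None of these says how a TRSAE-free death is scored in the primary test.

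On early TRSAEs, section 3.4.2.4 opens with logistical causes, so it may not be meant for infusions stopped for toxicity. Section 11.3.2 allows replacement for drop-out unrelated to treatment, which points the same way. The stopping rule is also not expressly limited to evaluable subjects. If it counts everyone treated, a removed TRSAE still moves the trial toward stopping and the inflation in step 4 does not arise. The wording leaves all of this open, and the non-evaluability sentence itself names no exception.

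**Conclusion.** The point holds as a mismatch between endpoint and decision rule, plus an evaluability gap for early TRSAEs. It should be fixed before analysis. The same 23 subjects can give opposite primary conclusions under two rules that are both in the plan, and no other section chooses between them.

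The examples in step 3 need no assumed rates, but they show what can happen, not how often. The 13% type I error rests on an assumed quarter of TRSAE subjects being lost, on 23 being analysed, and on those subjects also being left out of the stopping count.

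The 89.5% power is correct for 23 evaluable subjects with p as freedom from TRSAE. Only if a composite of alive and TRSAE-free was intended would it need restating. As an illustration, take the 95% as TRSAE-freedom alone and assume independent TRSAE-free death rates d of 2%, 5% and 10%. Then p=0.95×(1−d) is 0.931, 0.9025 and 0.855, and power at 21/23 is 79%, 61% and 33%. The documents give no such rates.

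**What to change.** 1. In the précis and sections 11.1, 11.3.2 and 11.3.4.2, state one endpoint, freedom from TRSAE, with one time window. Use that window for both the test and the three-subject boundary.
2. In sections 3.4.2.4 and 11.3.3, state that any subject who received BMSC and had a TRSAE is evaluable, counts as a failure and is never replaced.
3. State that TRSAE-free subjects who die or withdraw before the window ends are non-evaluable and replaceable within the planned 25. Report them separately, and prespecify one sensitivity analysis that counts them as failures.
4. Use the exact critical value for the number analysed (21/22 at n=22, power 69.8%), and note that the boundary matches the test at the planned 23 but not at 22. Keep 89.5% for n=23.
5. If a composite with survival was intended, justify the 95% for that composite and restate the power.

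The cost is wording in six places and one sensitivity analysis, with no added patients. Early TRSAEs will be handled less favourably to the treatment than the present wording allows. If more than two subjects become non-evaluable, fewer than 23 are analysed and power falls as in item 4.

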3.1.1 Accrual Objective

Twenty-five (25) patients will be accrued with the goal of attaining twenty-three (23) evaluable patients.

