11.3.3 Subject Replacement

Subjects who do not complete at least two doses of BMSCs will be replaced in this study.

15-H-0088

[name].

Abbreviated Title: Early BMSC Pilot for Acute GVHD

Version Date: 6/16/2016

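### The rules on replacement and evaluability differ between sections, could remove a TRSAE from the primary endpoint, and can leave fewer than 23 analysed, where the 21-of-23 cut-off no longer applies and power drops to about 70%

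*Combined protocol and SAP*

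**What the plan says.** - Section 3.1.1: "Twenty-five (25) patients will be accrued with the goal of attaining twenty-three (23) evaluable patients".
- Section 11.3.2: "a sample size of 23 subjects will achieve 89.5% power to test the above hypotheses using an exact binomial test". The null value is 75% and the test is run "with a one-sided significant level of 0.05". For planning, "we expect 95% subjects would reach day +56 without a TRSAE". To allow for drop-out unrelated to treatment, "up to 2 additional subjects may be enrolled to replace those subjects that are non-evaluable", so accrual totals 25.
- Section 11.3.3: "Subjects who do not complete at least two doses of BMSCs will be replaced in this study". It gives no maximum and does not refer to 11.3.2.
- Section 3.4.2.4: up to four infusions may be missed. A subject who misses more leaves treatment and is not evaluable for the primary endpoint.
- Sections 8.3 and 9.1.1: a subject with a TRSAE receives no further infusions.
- Section 11.3.4.2: the trial stops once three subjects have had a TRSAE, because "at least 21 of 23 subjects without a TRSAE are needed to reject the null hypothesis". No cut-off is given for any other number analysed.

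**The concern.** The three rules use different triggers. A subject who receives three doses and then misses more than four is replaceable under 11.3.2 but is not named in 11.3.3. A subject with one dose is replaced under 11.3.3, whatever the reason for stopping. For a third such subject, 11.3.3 calls for a replacement that the total of 25 does not allow.

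Two things are at stake. First, the primary endpoint is a safety event, and that same event ends treatment. A rule that replaces subjects for having too few doses can therefore act on the very subjects who had the event. Second, the cut-off of 21 of 23 sits just under the 0.05 limit. One analysed subject fewer changes the number of TRSAE subjects that the test can tolerate from two to one.

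**Working it through.** **Inputs.** Null proportion 0.75, expected proportion 0.95, one-sided alpha 0.05, exact binomial test, n = 23, total accrual 25 (11.3.2 and 3.1.1); cut-off 21 of 23 (11.3.4.2).

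**Formula.** With X the number without a TRSAE, P(X ≥ r) = Σ C(n,k) p^k (1−p)^(n−k), summed over k = r to n. Setting p = 0.75 gives the type I error and p = 0.95 gives the power.

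**The plan's own figure.** For n = 23 and r = 21, the type I error is 0.0492 and the power 0.8948. For r = 20 the type I error is 0.137, so 21 is the smallest valid cut-off. The stated 89.5% and 21 of 23 are both reproduced.

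**Three non-evaluable subjects under the total of 25.** This leaves 25 − 3 = 22.

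- 20 of 22 at p = 0.75: C(22,2)·0.75^20·0.25² + P(X ≥ 21) = 0.0458 + 0.0149 = 0.0607, which is above 0.05.
- 21 of 22 at p = 0.75: 0.0149, the valid cut-off.
- Power at 21 of 22: 22·0.95^21·0.05 + 0.95^22 = 0.3746 + 0.3235 = 0.698.

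**By number analysed:**

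| n | p with 2 TRSAE subjects | TRSAE subjects allowed | Actual alpha | Power |
|---|---|---|---|---|
| 25 | 0.032 | 2 | 0.032 | 87.3% |
| 24 | 0.040 | 2 | 0.040 | 88.4% |
| 23 | 0.049 | 2 | 0.049 | 89.5% |
| 22 | 0.061 | 1 | 0.015 | 69.8% |
| 21 | 0.075 | 1 | 0.019 | 71.7% |
| 20 | 0.091 | 1 | 0.024 | 73.6% |
| 19 | 0.111 | 1 | 0.031 | 75.5% |
| 18 | 0.135 | 1 | 0.039 | 77.4% |

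**The stop at three.** With n = 22 and three TRSAE subjects, 19 of 22 gives p = 0.162, so H0 is still not rejected and the stop is valid. But if only 22 will be analysed, rejection is already out of reach at the second TRSAE subject.

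**Chance of more than two losses in 25.** No rate is given, so the loss per subject q is an assumption: 1 − Σ C(25,k) q^k (1−q)^(25−k), k = 0 to 2. For q = 5%, 10% and 15% this is 0.127, 0.463 and 0.746.

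**Losing an event through replacement.** Suppose three infused subjects have a TRSAE, one of them after the first dose, and that subject is replaced and not counted. The analysis then shows 21 of 23, p = 0.049, and rejects. With all 24 infused subjects it is 21 of 24, p = 0.115, and does not. The stop at three prevents this only if the replaced subject counts towards it, which the text does not settle.

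Section 3.4.2.4 could act the same way. Treatment ended by a TRSAE after dose 3 leaves 8 − 3 = 5 of the first eight infusions ungiven, more than four. Whether infusions withheld for toxicity count as missed is not stated.

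**The case against.** Several stronger readings are tempting, and the documents do not support them.

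- **That 11.3.3 is uncapped.** It is silent on a maximum, and the total of 25 is stated in two other places. The sections can be read together, with 11.3.2 setting the limit and 11.3.3 naming one group to be replaced. This stands. It is also the reading under which 22 or fewer can be analysed.
- **That the rule in 11.3.4.2 is wrong at 22, or that success could be claimed at an alpha of 0.061.** The stop at three holds at 22 and at every smaller number. The rejection cut-off is given for 23 only, and 11.3.2 prespecifies an exact test at 0.05. Run on 22 subjects with two TRSAEs, that test does not reject. Inflated alpha would require ignoring the test.
- **That more than two losses are likely.** No drop-out rate is given, and four missed infusions are tolerated. The result depends wholly on the assumed rate.
- **That subjects with a TRSAE will be replaced.** Section 11.3.2 speaks of drop-out unrelated to treatment, which suggests that this is not intended. But 11.3.3 makes no such exception.

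The practical effect is also conditional. The decision at 22 differs from that at 23 only with exactly two TRSAE subjects, a chance of 0.905 − 0.698 = 20.7% if the true proportion is 95%. Multiplied by the chance of more than two losses, that is about 0.127 × 0.207 = 2.6% at 5% loss and at most 0.463 × 0.207 = 9.6% at 10% loss (the 20.7% falls slightly at 21 and 20). Much of the fall in power is discreteness, since actual alpha drops to 0.015. All of this stands and limits the severity. It does not supply the missing cut-off or the missing analysis set.

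**Conclusion.** The point holds at moderate severity. The plan has three rules on replacement and evaluability that do not match, and it defines no primary analysis set that keeps a subject whose early TRSAE ended treatment. If the total of 25 governs and three are non-evaluable, the valid cut-off is 21 of 22 and power is 69.8%; it is 71.7% at 21 and 73.6% at 20. These figures rest on the plan's own 75% and 95%. How often the situation arises rests on an assumed loss rate. The figures stated for 23 subjects are not in error.

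**What to change.** 1. Define the primary safety analysis set as every subject who received at least one BMSC infusion. Count every TRSAE in that set, whatever the number of doses received. State how a subject who leaves before day +56 without a TRSAE is counted. If such a subject counts as a failure, word the cut-off in terms of failures and not of TRSAE subjects alone.
2. Amend 3.4.2.4 and 11.3.3 to match. Missed infusions or fewer than two doses should bear only on response evaluability and replacement, and should never remove an infused subject from the primary endpoint. Make 11.3.3 subject to the total of 25. Unless more than two of the 25 are never infused, the analysed number then stays at 23 to 25.
3. In 11.3.4.2, keep the stop at three and give the rejection cut-off by number analysed: at most two TRSAE subjects for 23 to 25 (power 89.5%, 88.4%, 87.3%) and at most one for 18 to 22 (power about 70% to 77%). Fix this before the analysed number is known.

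The cost is a few sentences and no extra patients. Stated power becomes 87% to 88% if 24 or 25 are analysed, and the set will include some subjects with little exposure.
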